### 8.3.5 Pregnancy

Details of pregnancies in female partners of male patient will be collected after first exposure to trial product and until end of trial (follow-up) visit.

If a female partner of a male patient becomes pregnant **and** the outcome of the pregnancy is abnormal, the investigator should inform Novo Nordisk within 14 calendar days of learning of the abnormal outcome and should follow the procedures outlined in [Appendix 4](#).

### 8.3.6 Disease-related events and/or disease-related outcomes not qualifying as an AE or SAE

The following disease-related events (DREs) are common in patients with haemophilia A and can be serious/life threatening:

- Bleeding episodes.

#### Bleeding episodes

Because bleeding episodes are typically associated with the disease under study, they will not be reported according to the standard process for reporting of AEs/SAEs, even though the episodes may meet the definition of an AE/SAE. These episodes will be recorded in the patient diary and eCRF. These DREs will be monitored by Novo Nordisk on a routine basis.

*Note: The bleeding episode must be recorded and reported both as a DRE and as an AE/SAE if one of the following applies:*

- The bleeding episode is, in the investigator's opinion, of greater intensity, frequency, or duration than expected for the individual patient.
- The investigator considers that there is a reasonable possibility that the bleeding episode was related to treatment with the IMP.
- The bleeding episode is considered life-threatening (see [Appendix 4](#) for definition of life-threatening).
- The bleeding episode results in death.

### 8.3.7 Technical complaints

Technical complaints will be collected for all products listed on the technical complaint form.

Instructions for reporting technical complaints can be found in [Appendix 5](#).

In order for Novo Nordisk to perform a complete investigation of reported SAEs, Novo Nordisk might ask the investigator to complete a technical complaint form.

## 8.4 Treatment of overdose

Accidental overdose must be reported as a medication error. Intentional overdose must be reported as misuse and abuse, please refer to Section [8.3](#) and [Appendix 3](#) for further details.

In the event of an overdose, the investigator should closely monitor the patient for overdose-related AE/SAE.

For more information on overdose, also consult the current version of the turoctocog alfa pegol (N8-GP) investigator's brochure.[17](#)

## 8.5 Pharmacokinetics

Patients will be administered a single i.v. bolus injection of 50 IU/kg of N8-GP at Visit 2a and at Visit 7. The PK sessions extends over 96 hours. Overnight stay is not required. After completion of the PK sessions the patients will return to prophylaxis treatment with the next visit in line.

Patients must not have received current FVIII product for at least 4 days (96 hours) prior to the administration of trial product for the single-dose PK session at visit 2a, (i.e., a wash-out period of at least 96 hours must be applied before visit 2a).

There is no wash-out period for the steady-state PK session at visit 7, however administration of trial product at visit 7 should be approximately 96 hours after the previous N8-GP dose.

Patients must not be actively bleeding during the pharmacokinetic sessions.

The lines/tubes must be flushed immediately after administration of the trial product.

The pharmacokinetic endpoints (see Section [3.2.2.3](#)) will be based on assessments performed from 1 hour prior to and up to 96 hours after administration of N8-GP at Visit 2a (single-dose PK assessments) and Visit 7 (steady-state PK assessments) (see flowchart for PK assessments in Section [1.2](#)).

### 8.5.1 Visit 2a for patients undergoing PK assessments

Visit 2a should take place as soon as possible upon confirmation of eligibility approximately 2 weeks after the screening visit (Visit 1). Overnight stay is not required during the PK evaluation.

At Visit 2a the patients will receive their first dose of N8-GP (50 IU/kg) at the site and nine PK samples will be taken during the following 96 hours. If a bleeding episode occurs between Visit 2a and 2b the patient must contact the site and preferably come to the site for treatment with N8-GP. Further blood sampling for PK will be stopped. If the patient experiences a bleeding episode at home that requires immediate treatment, or if the investigator judges it as necessary, the patient must treat himself at home with his previous FVIII product. Treatment with previous FVIII product

must lead to immediate stop of PK assessments and the patient must be discontinued from treatment with trial product.

Assessments at visit 2a are outlined in Section [1.2](#) and additional assessments and sampling for PK patients are outlined in [Table 1-1](#).

The lines must be flushed immediately after administration of the trial product.

Samples taken pre-dose may be taken from the same arm as the one used for N8-GP administration.

The samples taken 30 min post dose must not be taken from the same vein as used for administration of N8-GP.

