### 6.5.1 Prohibited Medication

The following medications are **not** allowed during the course of the trial until after the End of Treatment visit.

- Bypassing products: activated recombinant factor VII (rFVIIa), plasma-derived prothrombin complex concentrates (pd-PCC) and plasma-derived activated prothrombin complex concentrates (pd-aPCC).
- Coagulation Factors: FVIII, FIX and FVII-containing products other than N8-GP and other FVIII-containing products like fresh frozen plasma or cryoprecipitate (exception: current FVIII is allowed until 96 hours before Visit 2a).
- Anti-coagulants such as Heparin and vitamin-K antagonists. Heparin is allowed for sealing of central venous access devices according to local practice.

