#### 8.1.1 Bleeding Episodes

From Visit 2a (inclusion of the patient and first administration of trial product) and during the entire trial period all treatment-requiring bleeding episodes (also referred to as 'bleeding episodes' or 'bleeds') must be entered by the patient or caregiver in the patient's diary. In case a patient is unable to enter a bleeding episode in the diary or is hospitalised, the investigator will report the bleeding episode in the eCRF (refer to Section [8.7](#) for reporting in the diary and eCRF).

If a patient experiences a bleeding episode at home, treatment with N8-GP should be initiated irrespective of severity of the bleeding episode (refer to Section [8.8](#) for training in home treatment). If the bleed is mild/moderate, the treatment responsibility is with the patient, patient's caregiver(s) and/or the investigator. For severe bleeding episodes, the treatment responsibility is always with the investigator and the patient should contact the site for further instructions. Treatment of severe

bleeding episodes should be initiated as soon as possible by the patient or caregiver. It is the responsibility of the investigator to assess the severity of the bleeding episodes and to ensure that all data is recorded correctly in the patient's diary.

Any discrepancy observed by the investigator or site staff must be documented in the patient's medical record and the patient must be retrained on completion of the diary completion, if required.

Joint bleeds are either categorised as target joint or non-target joint bleeds. Target joints are defined as 3 or more bleeding episodes in the same joint within 6 months. When there has been no bleed in the same joint for 12 months, such a joint is no longer considered a target joint.

A need for haemostatic rescue therapy with another FVIII product will be assessed by the investigator via phone or during the site visit. Patients treated with FVIII products other than N8-GP must be discontinued from treatment with N8-GP (exception: the patient's current FVIII product is allowed until 96 hours before visit 2a).

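### For a PK patient's home bleed needing immediate treatment between visits 2a and 2b, protocol 8.5.1 requires the previous FVIII product while 8.1.1 directs N8-GP

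*Protocol*

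**What the plan says.** **Protocol 8.5.1 (PK patients, visit 2a to 2b).** For a bleed in this window, "the patient must contact the site and preferably come to the site for treatment with N8-GP". PK sampling ends for any such bleed: "Further blood sampling for PK will be stopped". A second rule follows for home treatment. Its condition is "If the patient experiences a bleeding episode at home that requires immediate treatment, or if the investigator judges it as necessary", and its instruction is that "the patient must treat himself at home with his previous FVIII product". Using that product "must lead to immediate stop of PK assessments and the patient must be discontinued from treatment with trial product".

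**Protocol 8.1.1 (all patients, from visit 2a).** "If a patient experiences a bleeding episode at home, treatment with N8-GP should be initiated irrespective of severity of the bleeding episode". The section later says that the investigator assesses, by phone or at the site, any need for haemostatic rescue with another FVIII product. A patient given such a product is discontinued from N8-GP.

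**Protocol 6.5.1.** Other FVIII products are among the medicines not "allowed during the course of the trial until after the End of Treatment visit". The stated FVIII exception is that "current FVIII is allowed until 96 hours before Visit 2a".

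**Protocol 4.1.4.** Another FVIII product may be used, at the investigator's discretion, once 48 hours of adequate N8-GP dosing have failed to give a haemostatic response.

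**The concern.** A PK patient at home with an urgent bleed, and the site advising him, need one instruction. The current text gives two, naming different products, and they have different consequences for the trial. Under 8.5.1 trial treatment ends within four days of the first dose, and 7.2.1 rules out a replacement. Under 8.1.1 the patient is treated with trial product and continues. At stake are clear instructions for an urgent bleed and the retention of patients in a trial of 36.

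**Working it through.** The plan gives no figure to reproduce here, and 9.2 says that no formal sample size calculation was made. The check compares the texts and then sizes the consequence.

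**Comparing the texts**

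| | 8.5.1 | 8.1.1 |
|---|---|---|
| Who | PK patients | All patients, no PK exception |
| When | Visit 2a to 2b | From visit 2a |
| Event | Home bleed needing immediate treatment | Home bleed of any severity |
| Product | Previous FVIII product (must) | N8-GP (should) |
| Consequence | Trial product discontinued | Trial treatment continues |

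The 8.5.1 event lies wholly inside the 8.1.1 event, so both instructions apply to it.

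- Section 6.5.1 does not resolve this. Its FVIII exception has expired before visit 2a. It is supporting evidence only, because it also carries no exception for the 4.1.4 route.
- Section 4.1.4 does not resolve it either. Its route opens after 48 hours without response to N8-GP and so cannot cover a first, immediate treatment.
- Section 7.1 item 6 is not part of the conflict. It orders the same discontinuation as 8.5.1. The disagreement is over which product is used, not over what follows.

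**Could it happen?** Inputs: 15 PK patients (4.1, 9.2) and a 4-day window (flowchart, 1.2). The ABR in this population is not given. I use 1.18, the adult and adolescent median from the global programme (2.2), treated as a constant rate, and assumed values of 2.5 and 5.

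Window exposure = 15 × 4 / 365.25 = 0.164 patient-years. Expected bleeds = 0.164 × ABR. P(at least one) = 1 − exp(−expected bleeds).

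| Assumed ABR | Expected bleeds | P(at least one) |
|---|---|---|
| 1.18 | 0.19 | 18% |
| 2.5 | 0.41 | 34% |
| 5 | 0.82 | 56% |

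At each assumed rate this is an upper bound on use of the previous product, because 8.5.1 prefers treatment at the site and only some bleeds would need immediate treatment at home.

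**What one case costs under 8.5.1**

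- Planned treatment: 28 × 7 = 196 days. The bleed falls by day 4, so at least 196 − 4 = 192 days are lost. Against all planned exposure this is 192 / (36 × 196) = 192 / 7,056 = 2.7%.
- Spare patients: 36 enrolled − 30 required completers = 6, so one case uses 1 of 6.
- Overall ABR: with 35 patients at 196 days and one at 4 days, exposure is (35 × 196 + 4) / 365.25 = 18.79 patient-years. One bleed more or less moves the ABR by 1 / 18.79 = 0.053.

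**The case against.** The strongest reply is that the specific rule governs the general one. Section 8.5.1 is headed for PK patients, covers four days and says must; 8.1.1 is general and says should. Section 8.1.1 also points to the home-treatment training in 8.8, which may only just have begun, and 8.5.2 gives PK patients their second dose at the site. They may therefore hold no N8-GP at home before visit 2b. This may be what was intended, but the documents do not say so. Section 6.1 calls visit 2a the first dispensing visit, and 8.8 lets training start after the first site dose, neither with a PK exception. Sections 8.1.1 and 6.5.1 each print an exception for the current FVIII product, and neither reaches this window or refers to 8.5.1.

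A second reply stands in part. A reader might infer that both triggers in 8.5.1 clash equally with 8.1.1. They do not. Where the trigger is the investigator's judgement, 8.1.1 also lets the investigator assess rescue with another FVIII product, with no 48-hour condition and with discontinuation to follow. The two sections largely agree there. The clear conflict is confined to the immediate-treatment trigger.

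A reader might also infer from the version 4.0 summary of changes, which removed a visit 2a to 2b exception from four sections without listing 8.5.1, that 8.5.1 was overlooked. The summary cannot show this. It describes superseded text, and the change fits equally well as bringing those sections into line with the discontinuation that 8.5.1 orders.

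**Conclusion.** The conflict holds in the current text, for one event: a PK patient's home bleed between visits 2a and 2b that needs immediate treatment. It should be corrected, because it concerns treatment of an urgent bleed and decides whether a patient who cannot be replaced stays on trial product.

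Its statistical weight is modest. The case may well never arise: 18% to 56% is the upper-bound range for even one bleed, and it rests on assumed ABRs and a constant bleeding rate. A reader might infer that the conflict threatens the target of 12 complete PK profiles. It does not add to that risk, since 8.5.1 stops sampling for any bleed in the window whichever product is used. The primary estimate would move little, and no hypothesis is tested.

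**What to change.** Reconcile 8.5.1 with 8.1.1 and 6.5.1 so that one instruction applies between visits 2a and 2b. If a PK-specific exception is intended, state it in 8.1.1 and 6.5.1 with a cross-reference to 8.5.1, and say whether PK patients hold N8-GP at home before visit 2b. Which instruction stands is for the sponsor to decide.

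The cost is one protocol clarification and matching wording in site and patient instructions. It needs no new data and no change to the SAP.

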### **8.5.2 Visit 2b for patients undergoing PK assessments**

The second dose of N8-GP will be administered at the site after the last PK sample in relation to Visit 2a is taken.

Assessments at visit 2b are outlined in Section [1.2](#) and additional assessments and sampling for PK patients are outlined in [Table 1-1](#).

### **8.5.3 Visit 7 for patients undergoing PK assessments**

Patients who underwent a single-dose PK assessment at Visit 2a must also undergo a steady-state PK assessment at Visit 7. The steady-state PK session should be performed approximately 96 hours after the previous N8-GP dose. Overnight stay is not required during the PK evaluation. Blood sampling for PK should be stopped if a treatment requiring bleeding episode occurs during the PK session.

Samples taken pre-dose may be taken from the same arm as the one used for N8-GP administration.

The lines used for injection must be flushed immediately after administration of the trial product.

The samples taken 30 min post dose must not be taken from the same vein as previously used for administration of N8-GP.

Assessments at visit 7 and additional assessments and sampling for PK patients are outlined in Section [1.2](#).

## 8.6 Immunogenicity assessments

### 8.6.1 FVIII inhibitors

All patients will be examined for the development of FVIII inhibitors at scheduled visits (see Section [1.2](#)). If FVIII inhibitor development is suspected (e.g., increased number of bleeding episodes, bleeding episodes difficult to treat, N8-GP recovery and trough levels below expected values) during the course of the trial, additional inhibitor tests can be taken. All inhibitor tests must be analysed by the central laboratory.

A positive inhibitor test is defined as  $\geq 0.6$  BU. In the event that a previously inhibitor negative patient has a positive inhibitor test ( $\geq 0.6$  BU), the patient will be requested to visit the site for additional sampling preferably within 2 weeks. In addition, the following tests should be performed: anti-N8-GP antibodies, anti-PEG antibodies, FVIII trough (pre-dose), FVIII recovery (30 min post-dose) and lupus anticoagulant. These samples should preferably be taken prior to any change of treatment, and after approximately 96 hours wash-out period. If the second (confirmatory) inhibitor test is also positive, the patient must be discontinued from trial treatment if FVIII inhibitor  $>5$  BU or if FVIII inhibitor  $\geq 0.6$  and  $\leq 5$  BU that makes treatment (prophylaxis or treatment of bleeding episodes) with N8-GP clinically ineffective, by discontinuing trial product and attending the discontinuation of treatment visit (visit 7a) within 1 week after the result is available.

If the second (confirmatory) inhibitor test is positive and  $\leq 5$  BU and the investigator judges that the inhibitor does not clinically interfere with N8-GP treatment (prophylaxis or treatment of bleeding episodes), the patient can stay in the trial and continue treatment as per-protocol treatment.

A patient has inhibitor ( $\geq 0.6$  BU) if the patient has been tested positive for inhibitors at two consecutive test samples performed at the central laboratory preferably with no more than 2 weeks between the tests.

For patients discontinued from treatment with N8-GP: A follow-up visit must be scheduled 30(+5) days after the discontinuation of treatment (Visit 7a) and additional follow-up contact(s) (e.g., phone calls) may be arranged as long as clinically warranted up to 3 months after the EOT Visit.

For patients continuing in the trial with inhibitor ( $\geq 0.6$  and  $\leq 5$  BU): the patient must follow per-protocol treatment schedule and the scheduled visits as described in Section [1.2](#). Additional visits can be scheduled if closer monitoring is needed. Closer monitoring is highly recommended but this decision will be at investigator's discretion. In the event of a concern about reduced treatment efficacy a PK session may be performed. Blood sampling during the PK profile session can be performed at the following time points: pre-dose, 30 minutes ( $\pm 10$  min), 24h ( $\pm 8$  hours), 48h ( $\pm 8$  hours), 72h ( $\pm 8$  hours) and 96h ( $\pm 8$  hours).

A confirmed positive inhibitor is considered to have disappeared if the inhibitor titre is  $<0.6$  BU on 2 consecutive inhibitor tests (performed at 2 consecutive visits) and the FVIII recovery is  $\geq66\%$  of expected values. A patient with repeated positive inhibitor test result will count only once in the determination of the inhibitor incidence rate.

Patients who develop an inhibitor should be classified as high responders (peak inhibitor titre  $>5$  BU), low responders (peak inhibitor titre  $\leq5$  BU), and whether the inhibitor is transient (disappearing (inhibitor titre  $<0.6$  BU on  $\geq2$  consecutive measurements) spontaneously within 6 months without a change in treatment regimen), or not.

All per protocol inhibitor laboratory samples are to be analysed in the central laboratory, and only these results will be used in the data analyses.

Any single positive inhibitor test must be reported as an AESI (see Section [10.3.3](#)).

If the second (confirmatory) inhibitor test is positive then the event must be reported as an SAE (see Section [10.3.5](#)).

Blood samples for measurement of inhibitors towards FVIII will be analysed according to the Nijmegen modification of the Bethesda assay. Any sampling for the inhibitor test must be performed at least 96 hours after last administration of N8-GP to allow for maximum wash-out of the drug.

The patient may discontinue the trial including an EOT Visit and FU Visits or remain in the trial as described above. A patient having an initial positive inhibitor test and a second negative inhibitor test will be regarded as inhibitor negative and can continue in the trial.

If more than two patients are verified inhibitor positive an unscheduled Safety Committee Meeting will be called by Global Safety – and a decision whether to continue, modify or stop the trial will be made.

In the event that a patient is discontinued from trial treatment due to development of inhibitors, Novo Nordisk A/S will cover costs of associated treatment if the inhibitor development is considered a trial related injury in accordance with Chinese law.

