#### Footnotes

- a All screening assessments must be completed and evaluated by the investigator before the patient can be included in the trial.
- b Refer to [Table -1](#) for patients that will participate in PK assessments
- c To be measured pre-injection and 30 min (± 10min) post-injection.
- d If positive HIV test, then a HIV polymerase chain reaction (PCR) viral load assessment should be performed
- e Time from last treatment with current FVIII product should be at least 96 hours. The blood sample should be taken before any injection of N8-GP, if applicable.
- f Time from last treatment with N8-GP should be at least 96 hours. The blood sample should be taken before any injection of N8-GP, if applicable.
- g Only to be assessed in case of an acute, severe allergic/anaphylactic reaction.
- h Neurological assessments should not be performed for the assessments not performed at baseline (visit 2a).

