#### 4.1.4 Treatment of bleeding episodes

A treatment-requiring bleeding episode is defined as a bleed that requires treatment with N8-GP. If a patient experiences a treatment-requiring bleeding episode it must be treated as soon as it is identified. The investigator must always be contacted in case of a severe bleed and the patient should visit the site within 24 hours, or when possible. Mild/moderate bleeding episodes can be treated at home without contacting the site. Treatment should be started as soon as a bleed is identified.

For treatment of a mild or moderate bleeding episode, for example a joint bleed, N8-GP i.v. bolus injections at doses between 20-75 IU/kg BW should be administered to achieve a desired dose level based on the severity and location of the bleeding episode. Each unit of N8-GP will raise the FVIII level with approximately 2%. The required dose within the 20-75 IU/kg BW dosing range is determined by the investigator for every patient, using the recommendations in the World Federation of Haemophilia (WFH) guideline, FVIII activity should not fall below the lower range for the given plasma activity level (in % of normal or IU/dl) until the bleeding episode is resolved.

The effect of initial N8-GP dose on the clinical symptoms should be closely monitored and the need for a second dose should be evaluated within 8 hours after the initial N8-GP dose. If further doses are considered necessary to treat the bleeding episode, the patient is recommended to contact the investigator.

Any dose used for treatment of a bleed must be recorded as treatment of bleed and not as a prophylaxis dose. When the bleed has resolved (e.g. pain reduction and no increase in swelling), the patient can resume the prophylaxis dosing regimen.

If a bleeding episode occurs on a planned prophylaxis dosing day before administration of the prophylaxis dose, or if a bleeding episode extends into such a day, the bleeding episode must be treated with the full prophylaxis dose (this dose should be recorded as treatment of a bleeding episode). The patient should at all times follow the original prophylaxis dosing scheme unless a dose has already been given to treat a bleeding episode during the same day.

If a haemostatic response cannot be achieved after 48 hours using adequate doses of N8-GP treatment when treating bleeding episodes, another FVIII product may be used at the discretion of

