the investigator. The use of other FVIII products will result in discontinuation of the patient (exception: current FVIII product is allowed until 96 hours before visit 2a).

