### 7.1 Discontinuation of trial treatment

A patient who does not fulfil the eligibility criteria (inclusion/exclusion criteria) must not be included in the trial. Inclusion in violation of any of the eligibility criteria is non-compliant with Good Clinical Practice (GCP) procedures and must be reported to the sponsor without delay. This will be handled as an important protocol deviation, and the independent ethics committee (IEC)/institutional review board (IRB) and regulatory authorities must be notified according to local requirements. If there are no safety concerns for the patient, trial treatment may be continued or resumed at the discretion of the investigator after agreement with the sponsor's global medical expert.

A patient may be discontinued from treatment with N8-GP at the discretion of the investigator due to a safety concern.

The trial product must be discontinued, if any of the following applies for the patient:

1. Simultaneous use of an approved or non-approved investigational medicinal product in another clinical trial.
2. Haemostasis not achievable with N8-GP: The bleed cannot be controlled after 48 hours using adequate doses of N8-GP.
3. FVIII inhibitor ( $\geq 0.6$  and  $\leq 5$  BU) as confirmed by re-testing by Central Laboratory that makes treatment (prophylaxis and/or treatment of bleeding episodes) with N8-GP clinically ineffective. see section [8.6](#)

Protocol Trial ID: NN7088-4595	CONFIDENTIAL	Date: Version: Status: Page:	05 July 2021 4.0 Final 41 of 102	Novo Nordisk
-----------------------------------	---------------------	---------------------------------------	---	---------------------

4. FVIII inhibitor (>5 BU) as confirmed by re-testing by Central Laboratory.
5. Allergy/anaphylaxis to the trial product.
6. Use of Coagulation Factors FVIII, FIX and FVII-containing products other than N8-GP and other FVIII-containing products such as fresh frozen plasma or cryoprecipitate (**Exception:** FVIII is allowed until 96 hours before visit 2a).
7. Incapacity or unwillingness to follow the trial procedures.
8. Use of Anti-coagulants such as Heparin and vitamin-K antagonists (Heparin is allowed for sealing of central venous access devices according to local practice).

See Section [1.2](#) for data to be collected at the time of treatment discontinuation (discontinuation of treatment visit; Visit 7a) and follow-up and for any further evaluations that need to be completed.

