The purpose of the end of trial (follow-up) visit is to collect information about adverse events. For convenience of the patient the visit can be performed as a telephone contact.

The primary reason for discontinuation of trial product must be specified in the end-of-treatment-form in the eCRF, and final drug accountability must be performed. A treatment discontinuation session must be made in the IWRS.

If a patient discontinues treatment prior to Visit 7, Visit 7a should be performed as soon as possible after the last dose of trial product has been administered, and prior to starting treatment with another marketed product. The follow-up visit (Visit P8) should be performed 30 +5 days after the last dose of trial product has been administered. Even if treatment with trial product has been discontinued, after Visit P8 the patient should continue to follow the planned visit schedule until having completed the end of treatment visit (Visit 7).

After Visit 7a, the following procedures/assessments should not be performed for patients who discontinue treatment:

- Trial product administration
- FVIII activity
- Medication error
- Technical complaint
- Drug dispensing and drug accountability

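### The 96-hour wash-out before inhibitor samples names only N8-GP, so a patient who stops because he used another FVIII product can be sampled at visit 7a with that product on board

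*Protocol*

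**What the plan says.** **Wash-out rule.** Protocol section 8.6.1: "Any sampling for the inhibitor test must be performed at least 96 hours after last administration of N8-GP to allow for maximum wash-out". Flowchart footnote f, which covers the inhibitor samples at visits 3 to 7 and 7a: "Time from last treatment with N8-GP should be at least 96 hours". Footnote e, which covers visits 1 and 2a: "Time from last treatment with current FVIII product should be at least 96 hours".

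**Routes to another FVIII product.** Section 4.1.4 says that, when 48 hours of adequate N8-GP have not achieved haemostasis, "another FVIII product may be used at the discretion of" the investigator, and then that "The use of other FVIII products will result in discontinuation of the patient". Criterion 6 in section 7.1 makes stopping mandatory after "Use of Coagulation Factors FVIII, FIX and FVII-containing products other than N8-GP". Section 8.5.1 says of a PK patient who bleeds at home between visits 2a and 2b and needs immediate treatment that "the patient must treat himself at home with his previous FVIII product"; he must then stop trial product.

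**Timing of visit 7a.** Section 7.1 asks for 7a as soon as possible after the last N8-GP dose and "prior to starting treatment with another marketed product".

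**Definition and analysis.** Under section 8.6.1 and SAP 5.4.2.1, an inhibitor needs two consecutive positive tests (0.6 BU or more). Section 8.6.1 treats a positive followed by a negative as no inhibitor. SAP 5.4.2.1 puts in the denominator patients with at least 50 exposures, plus those with fewer who have an inhibitor. SAP 5.1 sends data after P8 in discontinued patients to listings, with separate safety tables if 5 or more patients have such data.

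**The concern.** The stated purpose of the 96 hours is to clear infused drug before the inhibitor test. Footnote e shows that the sponsor wants the same clearance from another FVIII product. Once N8-GP has started, that part of the rule disappears. A site can follow footnote f and section 8.6.1 exactly and still draw the sample while the patient carries another FVIII product.

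The patient who matters most is the one given rescue after 48 hours without haemostasis. Section 8.6.1 itself lists bleeds that are difficult to treat as a reason to suspect an inhibitor, so he is among those for whom a clean test is most useful. At stake are a missed inhibitor in an individual patient and a slightly low inhibitor rate. A missed case would also not count towards the more than two verified inhibitor patients that trigger an unscheduled safety committee meeting.

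**Working it through.** The documents give no figure on this point, so there is nothing to reproduce. The check sets the rules side by side and adds simple arithmetic.

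**1. Which product each rule covers**

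| Sample | Source | 96 hours counted from |
|---|---|---|
| Visits 1, 2a | Footnote e | Current FVIII product |
| Visits 3 to 7, 7a | Footnote f | N8-GP only |
| Any sample | 8.6.1, wash-out sentence | N8-GP only |
| After a first positive | 8.6.1, confirmatory sampling | No product named; about 96 hours, preferred only |

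**2. Can the section 7.1 safeguard work?** For a planned switch, yes: 7a comes first and the new product follows. It cannot work under the rescue, criterion 6 or PK-session routes, because use of the other product precedes the decision to stop.

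**3. Gap at visit 7a.** Let t be the hours from the last N8-GP dose to the first dose of the other product. If the sample is drawn at the earliest permitted time, 96 hours after N8-GP, the gap from the other product is at most 96 − t:

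- t = 24: 96 − 24 = 72 hours
- t = 48: 96 − 48 = 48 hours
- t = 72: 96 − 72 = 24 hours

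Repeat doses shorten the gap further. Sampling later does not guarantee a longer gap, because no rule limits dosing with the other product before the sample.

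**4. How a false negative acts under the two-test definition**

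- Earlier tests negative, 7a falsely negative: no confirmatory sample is triggered.
- Earlier test positive, 7a is the second test and falsely negative: the patient is classed as having no inhibitor.
- 7a positive, confirmatory sample falsely negative on the new product: same result.

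**5. Direction of the effect on the rate.** Suppose x of n patients are counted as cases without this patient. With fewer than 50 exposures, detection gives (x + 1)/(n + 1) and a miss gives x/n; the first is larger whenever x < n. With 50 or more exposures he is already in n, and a miss gives x/n instead of (x + 1)/n. Both errors lower the rate.

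**6. Number of patients.** 36 planned − at least 30 completers = at most 6 early stoppers for any reason, if the completion target is met. The documents do not say how many would have used another FVIII product.

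**7. Could an early negative be recognised afterwards?** Only in part.

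- Date and time of the last coagulation factor are scheduled at visits 1 and 2a only.
- FVIII activity is dropped after 7a. It may be measured at 7a itself; the flowchart columns are hard to align in the available text.
- Concomitant medication gives start and stop dates, not dose times.
- Anti-N8-GP tests measure binding antibodies and are analysed at the end of the trial.
- No SAP rule says how to read such a negative.

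**The case against.** **One 7a result does not make or remove a case by itself.** This stands. Two consecutive positives are needed, so the result matters only by preventing confirmation or by overturning an earlier positive. A reader might infer that every 7a negative feeds straight into the reported rate. The definition does not support that.

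**The confirmatory sampling text names no product.** True, and it helps. But it applies only after a first positive, so a falsely negative first test never reaches it. It is also only a preference, and its wish to sample before a treatment change is already lost in these patients.

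**96 hours may be longer than another product needs.** Section 2.2 gives N8-GP a 1.6-fold longer half-life than standard FVIII and says no extended half-life recombinant product is available in China. On that basis 96/1.6 = 60 hours spans the same number of half-lives. A single dose at t = 24 leaves 72 hours, which exceeds 60; at t = 48 the gap is 48 hours, which does not. Repeat rescue dosing would shorten both, and footnote e still uses 96 hours for the current product. What stands is that a gap under 96 hours does not prove masking.

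**Two of the settings carry little weight.** This also stands. The PK-session patient has at least 150 earlier exposure days, no known inhibitor history, tests at visits 1 and 2a after wash-out, and normally a single N8-GP dose. Samples after P8 mainly reach listings.

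**Other data may reveal residual factor at 7a.** FVIII activity, if measured there, together with concomitant medication dates would help a careful reader. No rule requires that they be used.

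**Conclusion.** The gap is real and minor. For patients who stop N8-GP because they have already used another FVIII product, the wash-out rule protects against the wrong product alone, and the visit 7a timing rule cannot compensate. The rescue patient is the main case; the PK-session route and samples after P8 add little.

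The size is small and not quantified. It rests on three assumptions: that at least one such patient occurs, that he has an inhibitor, and that residual FVIII from the other product hides it. The third is inferred from the stated purpose of the wash-out; the documents give no size for it. If masking occurs, the error goes one way: a lower rate or a missed inhibitor.

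A reader might infer that inhibitor testing is unreliable in all discontinued patients, or that the trial's inhibitor rate is materially biased. The documents support neither. Planned switches are covered at 7a, at most 6 patients stop early if the target is met, most post-P8 data stay out of the main analysis, and no hypothesis is tested.

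**What to change.** Keep the unconditional 96 hours from N8-GP in footnote f and section 8.6.1, and add: *and at least 96 hours after any other FVIII product; if that gap is not clinically acceptable, sample immediately before the next dose of the other product*. The exception must apply to the other product only. If it reached N8-GP, patients on twice-weekly dosing, with doses 3 to 4 calendar days apart, could be sampled before 96 hours, which the present rule forbids.

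Record product, date and time of the last coagulation factor dose at visit 7a and at each later inhibitor sample.

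Add one SAP sentence: a negative drawn less than 96 hours after another FVIII product is flagged as inconclusive and does not by itself overturn an earlier positive.

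The cost is a phrase in two places, one repeated eCRF item, one SAP sentence and possibly a short delay of the 7a inhibitor sample. The delay pulls against holding 7a as soon as possible; the pre-dose exception limits it. No extra visits, assays or patients are needed.
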